## **9. STUDY PURPOSE AND OBJECTIVES**

### **9.1 Study Purpose**

The purpose of this study is to evaluate the tolerability, safety and immunogenicity of VLA2001 and to optimise the dose for phase II and III studies. Immunogenicity will be investigated in a larger study sample after safety has been demonstrated in this combined phase I/II study.

This study is being extended to investigate the tolerability, safety and immunogenicity of a booster vaccination with VLA2001.

### **9.2 Primary Objective**

- The primary objective of this study is to evaluate the tolerability, safety and immunogenicity of the inactivated, adjuvanted SARS-CoV-2 vaccine candidate VLA2001 up to 14 days after completion of a two-dose primary immunization schedule in healthy adults aged 18 to 55 years.

### **9.3 Secondary Objectives**

- 1) To determine the optimal dose level of inactivated, adjuvanted SARS-CoV-2 vaccine candidate VLA2001 in healthy adults aged 18 to 55 years.
- 2) To evaluate tolerability, safety and immunogenicity of the inactivated, adjuvanted SARS-CoV-2 vaccine candidate VLA2001 up to 6 months after the last vaccination in healthy adults aged 18 to 55 years.
- 3) To evaluate tolerability, safety and immunogenicity of a booster dose with vaccine candidates VLA2001 in healthy adults aged 18 to 55 years.

### **9.4 Exploratory Objective**

- To evaluate cellular immune response after vaccination with the inactivated, adjuvanted SARS-CoV-2 vaccine candidates VLA2001 after completion of a two-dose primary immunization schedule and after a booster vaccination.

## 10. STUDY DESIGN

### 10.1 Overall Study Design

This is a first-in-human phase I/II study that will evaluate three dose levels of VLA2001 (low, medium, high) for safety, tolerability and immunogenicity in a two-dose schedule in a healthy young adult population aged 18 to 55 years.

The study will be a randomised, double-blind, dose-escalation, multicentre study with three dose groups and 50 Participants recruited to each dose group. The study is conducted in three parts. Part A (Day 1 to Day 36), Part B (Day 37 to Day 208) followed by the Booster Phase: Part C (Visits 7 to 10).

Following an evaluation of Part A data (i.e. data up to Day 36) from the present study, further clinical studies will be initiated.

The study design for Study VLA2001-201 is illustrated in Section 22.1.

Assessments, including immunogenicity and solicited and unsolicited AEs, SAEs or AESIs will be performed at the time points specified in sections 22.2 and 22.3 (specific for Booster Phase) up to Visit 10 (6 months post booster). In addition, samples will be taken for later investigation of cellular immune responses and mucosal immune responses.

#### 10.1.1 Part A

For safety reasons, the first 15 participants will be included into the study in an open-label, not randomized manner following a staggered dose escalation of VLA2001. Dose escalation will be done at a single site to ensure permanent oversight on safety data by one principal investigator during the recruitment of the 15 sentinel Participants.

Dose escalation starts with the first vaccination of the first sentinel Participant in the low dose treatment group. After vaccination, the first Participant of a dosing group will be observed for the development of any acute reaction at the study site for 3 hours after the vaccination procedure. Prior to discharge from the study site, vital signs will be measured and the Participant will be instructed to use the e-Diary. The study site will contact the Participant per phone approximately 24 hours after vaccination to assess the safety status of the Participant. The provided information must be compared with the entries in the Participant's e-Diary. The minimum time before the next Participants are vaccinated is therefore 24 hours. The next 4 Participants of the same dosing group will be vaccinated at least with a one-hour interval between each Participant. These 4 Participants will be observed for 60 minutes at the study site to monitor for the development of acute reaction. Before discharge, vital signs will be measured and Participants will be instructed to use their e-Diaries. Safety telephone calls will be performed by the study site after approximately 48 hours after vaccination. After confirmation by the investigator that no stopping criteria (see Section 10.6) has been met, the procedure will be repeated with the first Participant of the next dose level. The minimum time before vaccination of a new dose level will be 48 hours.

A Data Safety and Monitoring Board (DSMB) will review the accrued safety data at Day 4 of all 15 sentinel Participants. After favourable DSMB review randomization of the remaining 135 Participants across all sites will be initiated.

The remaining 135 Participants will be enrolled, screened and randomised in a 1:1:1 fashion to the three dose groups in the blinded part of the study. Participants will be observed for 30 minutes post vaccination on Day 1. An unscheduled safety telephone call will be performed in case a Grade 3 AE or SAE will be reported by the Participant via e-Diary. All Participants will be followed by e-Diary for 7 days post vaccination, starting on the day of vaccination. Participants will return to the study site on Day 8 (Visit 2). After (approximately) 20 Participants per dose group have been randomised and followed up 7 days post first vaccination, and periodically up to Day 36 for all randomised Participants, the DSMB will review the accrued safety data. All Participants will receive their second vaccination on Day 22 (Visit 3) and will be followed up on Day 36 (Visit 4), 14 days after the second vaccination. The DSMB will review safety and immunogenicity data up to Day 36.

### **10.1.2 Part B**

All Participants will be further followed up on Day 106 (Visit 5) and Day 208 (Visit 6), 6 months after the second vaccination.

### **10.1.3 Part C (Booster Phase)**

During their Day 208/ Month 7 (Visit 6) study visit, all eligible participants will be invited to take part in the Booster Phase (Part C) to investigate tolerability, safety and immunogenicity of a booster dose of VLA2001 (high dose).

Due to planning considerations, all consenting participants will receive the Booster vaccination between mid to end September 2021 (Visit 7), this corresponds to about 8-9 months after completing the primary vaccination series.

Participants will be asked to return to the study site for a follow-up visit approximately two weeks after the booster vaccination then 1 month after the booster vaccination. Participants will be followed-up for safety during a phone call approximately 6 months after the booster vaccination.

A scheduled DSMB review will be performed once all vaccinated Participants have completed their Visit 7. Additional safety data review will occur when necessary (ad-hoc) as defined in the DSMB Charter. A final review of generated safety data will be performed by the DSMB once all participants have completed this clinical study.

## **10.2 Study Duration**

The overall study duration (First Participant In [FSI] –Last Participant Out [LSO]) is estimated to be approximately 16 months. Individual Participant participation is approximately 15

months from enrolment (i.e. Informed Consent signed) to study completion unless the study is prematurely discontinued.

Part A of the study will be completed when the last Participant has completed Day 36 (14 days after the second vaccination). Part B of the study will be completed when the last Participant has completed Day 208 (6 months after the second vaccination). The Booster Phase (Part C) will be completed when the last participant has completed the safety follow-up call 6 months (Visit 10) after the Booster vaccination.

## 10.3 Study Endpoints

### 10.3.1 Safety Endpoint

#### 10.3.1.1 Primary Endpoint

- Frequency and severity of solicited AEs (local and systemic reactions) within 7 days after any vaccination of the primary vaccination series.

#### 10.3.1.2 Secondary Endpoints

The following secondary tolerability and safety endpoints will be determined:

- Frequency and severity of any unsolicited AE until Day 36.
- Frequency and severity of any vaccine-related AE until Day 36.
- Frequency and severity of any AE until Day 208.
- Frequency and severity of any vaccine-related AE until Day 208.
- Frequency and severity of any SAE until Day 36.
- Frequency and severity of any AESI until Day 36.
- Frequency and severity of any SAE until Day 208.
- Frequency and severity of an AESI until Day 208.

#### Booster Phase:

- Frequency and severity of solicited AEs (local and systemic reactions) within 7 days after the booster vaccination
- Frequency and severity of any unsolicited AE up to Visit 9
- Frequency and severity of any vaccine-related AE up to Visit 9
- Frequency and severity of any SAE up to Visit 10
- Frequency and severity of any AESI up to Visit 10

## 10.3.2 Immunogenicity Endpoints

### 10.3.2.1 Primary Endpoint

- Geometric mean titre (GMT) for neutralizing antibodies against SARS-CoV-2 determined by wild-type virus neutralizing assay at Day 36.

### 10.3.2.2 Secondary Endpoints

The following secondary immunogenicity endpoints will be evaluated:

- Immune response as measured by neutralizing antibody titres against SARS-CoV-2 on Day 8, Day 22, Day 106 and Day 208
- Proportion of Participants with seroconversion on Day 8, Day 22, Day 36, Day 106 and Day 208, in Participants negative for SARS-CoV-2 at Screening
- Fold increase of SARS-CoV-2 neutralizing antibody titres on Day 8, Day 22, Day 36, Day 106 and Day 208 compared with baseline
- GMTs for IgG against SARS-CoV-2, determined by ELISA, at Day 1, 8, 22, 36, 106, and 208.
- Proportion of Participants with seroconversion in terms of IgG antibodies against SARS-CoV-2 as determined by ELISA on Day 8, Day 22, Day 36, Day 106 and Day 208.

Booster Phase:

- Geometric mean fold rise (GMFR) from pre-booster time point (Visit 7) to 2 weeks after booster dose (Visit 8) with regards to neutralizing antibodies.
- Geometric mean fold rise (GMFR) from pre-booster time point (Visit 7) to 4 weeks after booster dose (Visit 9) with regards to neutralizing antibodies.
- Proportion of Participants with 4-fold increase from pre-booster dose (Visit 7) to 2 weeks after booster dose (Visit 8) with regards to neutralizing antibodies.
- Proportion of Participants with 4-fold increase from pre-booster dose (Visit 7) to 4 weeks after booster dose (Visit 9) with regards to neutralizing antibodies.
- Geometric mean titres (GMT) measured as neutralizing antibody titres against SARS-CoV-2 at Visit 7, Visit 8 and Visit 9.
- Geometric mean fold rise (GMFR) from pre-booster dose (Visit 7) to 4 weeks after booster dose (Visit 9) with regards to S-protein binding antibodies (ELISA).
- Geometric mean fold rise (GMFR) from pre-booster dose (Visit 7) to 2 weeks after booster dose (Visit 8) with regards to S-protein binding antibodies (ELISA).

- Proportion of Participants with 4-fold increase from pre-booster dose (Visit 7) to 4 weeks after booster dose (Visit 9) in regards to S-protein binding antibodies (measured by ELISA).
- Proportion of Participants with 4-fold increase from pre-booster dose (Visit 7) to 2 weeks after booster dose (Visit 8) in regards to S-protein binding antibodies (measured by ELISA).
- GMT measured as IgG antibodies against SARS-CoV-2, as determined by ELISA, at Visit 7, Visit 8 and Visit 9.

### 10.3.2.3 Exploratory Endpoint

- Cellular immune response on Day 1, Day 36, Day 208 and Visit 7 and Visit 8.

## 10.4 Justification for Study Design and Dosage

This phase I/II study is designed as a blinded, randomised, multicentre study to evaluate the safety, tolerability and immunogenicity of three dose levels of VLA2001. This study is being extended to investigate the safety, tolerability and immunogenicity of a booster vaccination with VLA2001.

VLA2001 is expected to have a safety profile comparable with that of other inactivated vaccines such as IXIARO. However, since this is a first-in-human study with VLA2001 the study will, as a safety precaution, begin with enrolment of 15 sentinel Participants (5 Participants per dosing group). This open-label dose escalation will be done at a single site to ensure permanent oversight on safety data by one principal investigator during the recruitment of the 15 sentinel Participants. Dose escalation starts with the first vaccination of the first sentinel Participant in the low dose treatment group. If no safety concern is detected, four further Participants are vaccinated after 24 hours within the same treatment group. At least a one-hour interval must be followed between vaccinations of Participants. If no safety concern is identified within 48 hours after vaccination, vaccinations in the medium dose level are initiated. Again only one Participant will receive the first medium-dose vaccination, if no safety concerns are identified, another four Participants will be enrolled after 24 hours in the same treatment group. The same process will be followed for the high-dose treatment group. Each of the 15 sentinel Participants will be observed on-site for at least 60 minutes following vaccination.

A Data Safety and Monitoring Board (DSMB) will review the accrued safety data after the sentinel Participants of the high dose group have passed their 3-days post vaccination time

point before randomization of further Participants across all sites will be initiated. The part of the study will be conducted double-blind in order to limit the introduction of a safety bias by the Participants and/or Investigator's staff performing medical safety assessments.

#### **10.4.1 Selection of Study Population**

The study will randomize approximately 150 healthy adult Participants aged 18 to 55 years. The proposed study population has been selected to conduct this first-in-human study in adults of good health. A maximum age limit of 55 years has been chosen in this first-in-human study in order to reduce the chance of observed adverse safety outcomes that might be due to medical conditions that are more likely to occur in older adults and were not identified prior to study entry.

#### **10.5 Randomisation and Blinding**

The first 15 Participants will be enrolled in the study in an open-label, not randomized dose-escalating manner. The remaining 135 Participants will be randomised in a blinded manner in a 1:1:1 fashion to the three dose groups on Day 1 as described in Section 10.1.

All participants who do not meet any exclusion criteria for a booster dose will be invited to receive a booster dose with VLA2001.

Each Participant will have a unique Participant screening number obtained from the interactive voice response system/interactive web response system (IXRS) assigned at the screening visit. The Investigator will keep a record (i.e. the Participant screening log) of Participants who entered screening.

The IMP will be prepared by study staff in accordance with the treatment allocation provided in the IXRS. An overview of persons who will be (un)blinded is provided below:

##### Unblinded:

- Fifteen sentinel Participants.
- Members of the DSMB.
- Unblinded statistician(s) at CRO (Pharm-Olam) who will be responsible for following tasks:
  - Generation of the randomization code list
  - Attendance of unblinded sessions of DSMB meetings
  - Generating safety data tables/listings/figures for the DSMB meetings

##### Blinded:

- The 135 Participants in the randomised part of the study.
- Investigators and other site staff
- Biostatisticians writing the Statistical Analysis Plan and developing the statistical analysis.
- Clinical research associates (CRAs) responsible for monitoring study data.
- All laboratory personnel at central laboratories for safety and immunogenicity laboratory assessments.
- All other Sponsor and contract research organisation (CRO) staff not otherwise specified above will be unblinded as part of the Part A statistical analysis. Laboratory personnel at the Sponsor's testing labs remain blinded throughout the study for additional testing procedures.

### 10.5.1 Blinding Process

IMP will be provided to the study sites in a blinded manner, i.e. no visual differentiation will be possible, same volumes will have to be administered for all dose groups. Identification of and allocation of the syringe to a specific Participant is ensured by placing a tear-off label containing a kit number, Participant number, date of injection and operator onto the label.

Booster phase:  
VAL2001 vaccine will be administered as open label.

Further details are presented in the IMP Manual.

### 10.5.2 Unblinding

The randomisation assignment is not to be revealed except in emergency cases where unblinding is necessary for the clinical management of an AE/SAE. In such events, the Investigator must either inform the Sponsor before breaking the blind or immediately after unblinding.

**In case of emergency, the vaccine administered to the Participants can be revealed through the web-response system (IXRS).**

### 10.6 Study stopping criteria

The DSMB can issue a recommendation to stop the study during ad-hoc DSMB meetings, or to discontinue a treatment group, e.g. in response to an excess rate of AEs with the same suspected underlying pathological mechanism.

Study vaccinations will be suspended, pending DSMB review and assessment, should any of the following criteria be met during the course of the study:

#### 10.6.1 During staggered dose escalation period:

- **One or more Participants** experience an SAE or AESI with no likelier alternative cause than the study vaccine (i.e. related).
- **One or more Participants** experience a severe systemic allergic reaction, e.g. generalized urticaria or anaphylaxis within 24 hours following vaccine administration, with no likelier alternative cause than the study vaccine.
- **One or more Participants** experience Grade 4 local reaction at the vaccination site, characterized by ulceration, necrosis or any Grade 4 local reaction that requires emergency medical care within seven days after study vaccine administration.
- **One or more Participants** in the same treatment group experience the same Grade 3 solicited local AE 48 hours following vaccination.
- **One or more Participants** in the same treatment group experience the same severe (Grade 3 or Grade 4) solicited systemic AE within 48 hours following vaccination, with no likelier alternative cause than the study vaccine.

#### 10.6.2 During entire study period (including the Booster phase):

- **One** or more Participants experience an SAE or AESI with no likelier alternative cause than the study vaccine (i.e. possibly or probably related).
- **Two** or more Participants experience a Grade 3 systemic allergic reaction, e.g. generalized urticaria within 10 days after vaccine administration, or anaphylaxis within 24 hours following vaccine administration, with no likelier alternative cause than the study vaccine.
- **Three** or more Participants in the same dose group experience the same Grade 3iv solicited injection site reaction that (1) occurs within 7 days following vaccination and (2) lasts longer than 3 days.

---

iv **Note:** for the purpose of this study, AEs graded as potentially life threatening (Grade 4) will be reported as SAEs (see Section 16.1.2) and will thus fall under the first criterion in Section 11.6.

- **Three** or more Participants in the same dose group experience the same Grade 3 solicited systemic reaction that (1) occurs within 7 days following vaccination, (2) lasts longer than 3 days, and (3) has no likelier alternative cause than the study vaccine.
- **Three** or more Participants in the same dose group experience the same Grade 3 unsolicited AE, including Grade 3 laboratory abnormalities that are assessed to be clinically relevant by the Investigator, that (1) occurs within 36 days following first vaccination, and (2) has no likelier alternative cause than the study vaccine.

Grade 3 and Grade 4 solicited and unsolicited AEs will be confirmed with the site prior to stopping the study due to a pre-defined stopping rule. If any of the above-mentioned criteria is met or the DSMB recommends halting the study or discontinuing a dose group for other reasons (e.g. in response to an excess rate of AEs with the same suspected underlying pathological mechanism), the Sponsor will notify the appropriate regulatory authorities and EC according to local requirements.

Prompt notification by the investigator to the sponsor of an SAE is essential so that legal obligations and ethical responsibilities towards the safety of participants and the safety of the study intervention under clinical intervention are met. The sponsor has a legal responsibility to notify both the local regulatory authority and other agencies about the safety of a study intervention under clinical investigation. The sponsor will comply with country-specific regulatory requirements relating safety reporting to the regulatory authority, IRBs/ECs, and investigators. Investigator safety reports must be prepared for SUSARs according to local regulatory requirements and sponsor policy and forwarded to investigators as necessary. An investigator who receives SUSARs or other specific safety information (e.g., summary or listing of SAEs) from the sponsor will review and then file it along the SRSD(s) for the study and will notify the IRB/EC, if appropriate according to local requirements.

If a study stopping rule is met, the DSMB will review all pertinent safety data to provide a recommendation for the study to continue/discontinue based on cumulative safety data evaluation and any other relevant data available at the time of review. Vaccination of Participants already enrolled in the study and restart of recruitment may only proceed after positive DSMB recommendation, and relevant regulatory authorities and EC will be informed.

The Sponsor or Investigator may also stop the study for any medical reason at any time.

If the Sponsor or Investigator decides to terminate the study before it is completed, they will notify each other in writing, stating the medical reason(s) for early termination. In terminating the study, the Sponsor and the Investigator will ensure that adequate consideration is given

to the protection of the Participants' interests. The Sponsor or Investigator will notify the relevant regulatory authorities or EC in writing in accordance with local requirements. Documentation will be submitted for filing in the Central and Investigator File and the Trial Master File.

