#### Booster Phase:

At Visit 6 (Month 7), all participants who previously had received two study vaccinations will be asked for their consent to take part in the Booster Phase (Part C). Independently of the dose received during the primary immunization, participants will receive a booster dose (high dose) of VLA2001.

The Booster vaccination will also be offered to participants who have either had a confirmed COVID-19 disease or who have received a national COVID-19 vaccination.

The Booster vaccination will be administered at Visit 7. Visit 7 is expected to be performed in September 2021. This timing will translate to the booster dose being given to the participants at approximately 8 to 9 Months after completion of the primary immunization schedule.

Participants will be asked to return to the study site for two follow-up visits, 2 weeks after the booster vaccination (visit 8) and one month after the booster vaccination (Visit 9).

6 months after the Booster vaccination, participants will be followed-up through a safety phone call. This telephone call is also the end of the study for the participants that consented to the booster part of the study.

Additional safety data review by the DSMB will occur when necessary (ad-hoc) as defined in the DSMB Charter. A final review of the generated safety data will be performed by the DSMB once all participants have completed the clinical study.

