#### **Responsibilities of the DSMB**

- Review of accrued safety data of the 15 sentinel Participants including safety data at least 3 days post vaccination of the high dose group to decide whether it is safe to proceed with recruitment.
- Review of accrued safety data of the first 60 randomised Participants (overall 20 Participants per dose group) including safety data at least 7 days post vaccination.
- Review of any case reports of SAEs/AESIs on an ad-hoc basis.
- Periodically review unblinded listings and summary tabulations of SAEs, deaths, solicited AEs, unsolicited AEs and AEs leading to withdrawal from further vaccinations.
- All cases of COVID-19 and severe COVID-19 will be assessed by the Sponsor and presented to the DSMB for adjudication against the case definitions.
- Participate in ad-hoc DSMB reviews initiated if enrolment is interrupted by the principal Investigator, the Sponsor or the medical monitor at the CRO for any safety reasons, or if a pre-specified study stopping rule applies.

The DSMB can issue a recommendation to stop the study during ad-hoc DSMB meetings, or to discontinue a treatment group, e.g. in response to an excess rate of AEs with the same suspected underlying pathological mechanism.

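### The fifth stopping criterion in Protocol 10.6.2 is said to cover the Booster phase, but its 36-day window runs from the first vaccination, so no post-booster event can meet it

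*Protocol*

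**What the plan says.** Protocol 10.6 sets the consequence of meeting a criterion: "Study vaccinations will be suspended, pending DSMB review and assessment". The criteria for everything after the sentinel stage are in 10.6.2, whose heading reads "During entire study period (including the Booster phase" and closes the bracket there. Five criteria follow. The fifth counts three or more cases in which "Participants in the same dose group experience the same Grade 3 unsolicited AE", clinically relevant Grade 3 laboratory abnormalities included, provided the event is one "that (1) occurs within 36 days following first vaccination, and (2) has no likelier alternative cause than the study vaccine".

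The same section adds "If a study stopping rule is met, the DSMB will review all pertinent safety data" and allows vaccination to resume only after a positive DSMB recommendation. Meeting a criterion also obliges the sponsor to notify the authorities and the ethics committee.

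On the booster, Protocol 10.1.3 places Visit 7 in the second half of September 2021 and states that "this corresponds to about 8-9 months after completing the primary vaccination series". The synopsis adds: "Independently of the dose received during the primary immunization, participants will receive a booster dose (high dose) of VLA2001". Neither document gives a booster version of the fifth criterion.

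**The concern.** The heading promises that all five criteria operate after the booster, but the fifth is tied to an event that is months past by then. A safety rule that cannot operate in a phase it names gives false assurance to anyone who reads the heading and the list together.

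The booster is a new exposure in this study: a third dose, supplied ready-mixed in multi-dose vials with rHA in place of HSA (Protocol 12.1.1 and 12.1.2), and offered also to people who have had COVID-19 or a national COVID-19 vaccine. Safety laboratory samples are drawn at Visits 8 and 9 (Protocol 22.3). If three boosted participants showed the same related Grade 3 abnormality, and it was neither an SAE nor an AESI, no pre-set rule would respond. Suspension would rest on someone choosing to act.

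**Working it through.** **Inputs**
- First vaccination on Day 1, second on Day 22 (Protocol 13.3.1; SAP 5.2.1 defines Day 1 the same way).
- Fifth-criterion window: 36 days from the first vaccination (Protocol 10.6.2).
- Booster at Visit 7, about 8 to 9 months after the second dose (Protocol 10.1.3). I take these as 243 and 274 days.
- Booster consent at Visit 6, Day 208 ± 14 days (Protocol synopsis and 22.3), so the booster cannot come earlier.
- Visit 8 at 14 ± 2 days and Visit 9 at 28 ± 7 days after the booster (Protocol 22.3).

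**Does any post-booster event fall inside the window?**
- Window closes: Day 1 + 36 = Day 37.
- Nominal booster: 22 + 243 = Day 265 to 22 + 274 = Day 296. Gap: 265 − 37 = 228 days to 296 − 37 = 259 days.
- Lower bound that needs no calendar dates: earliest Visit 6 = 208 − 14 = Day 194. Gap: 194 − 37 = 157 days.

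No permitted visit timing brings a post-booster event into the window.

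**How the other rules are anchored**
- Criterion 1 (related SAE or AESI): no time window.
- Criterion 2 (allergic reactions): counts from vaccine administration.
- Criteria 3 and 4 (prolonged Grade 3 solicited reactions): 7 days from vaccination, with no restriction to the first.
- Criterion 5: 36 days from the first vaccination only.
- The individual withdrawal rule for the same type of event (Protocol 11.6): 36 days after vaccination, without the word first, in a list that expressly covers the second and booster doses.

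Only criterion 5 is anchored in a way that excludes the booster. The contrast with 11.6 suggests wording carried over when the Booster Phase was added.

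**Doses an automatic suspension could still affect**
The protocol gives no exact dates. Assume planned dosing from 15 to 30 September 2021.
- On the planned dates: earliest Visit 8 samples on 15 September + 12 days = 27 September, 3 days before the last dose.
- With the ± 14-day Visit 7 window fully used: first dose 1 September, earliest samples 13 September, last dose 14 October, so 31 days before the last dose.

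**Would a 36-day window from the booster reach the laboratory visits?**
Latest Visit 8 = 14 + 2 = day 16. Latest Visit 9 = 28 + 7 = day 35. Both are within 36.

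**The case against.** The strongest reply is that little is lost.

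- **Criterion 1 overlaps heavily with criterion 5.** It fires on one related SAE or AESI and stays active after the booster. The AESI list in Protocol 22.5 includes thrombocytopenia, liver injury, acute kidney injury and coagulation disorder, so many related Grade 3 platelet, liver, kidney or clotting findings could suspend vaccination at one case rather than three. Grade 4 events are reported as SAEs.
- **Oversight continues.** The DSMB's duties in 15.11.3 include: "Periodically review unblinded listings and summary tabulations of SAEs, deaths, solicited AEs, unsolicited AEs". There are scheduled, ad-hoc and final DSMB reviews in the Booster Phase (10.1.3), sponsor review of listings (15.11.4), Grade 3 information to investigators (15.11.5) and safety calls after Grade 3 e-Diary entries (22.3). The sponsor or investigator may stop the study on medical grounds at any time, and a DSMB recommendation to halt also leads to notification.
- **Few doses are left to suspend.** The booster is one dose given over a short period.

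All of this stands, and it is why the point is minor. It does not close the gap. Grade 3 neutrophil or electrolyte results, for example, are graded in 22.4 but not listed in 22.5, and would not necessarily be SAEs. The scheduled booster review in 10.1.3 follows completion of Visit 7 by everyone vaccinated, so it comes after dosing ends and cannot act as a trigger during it.

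One might try to read the first vaccination as the booster itself. The protocol uses that phrase for Day 1 and names the later dose separately, so this reading is strained.

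A reader might also infer that moving the window would still leave the rule unworkable, because it counts within a dose group and everyone boosted receives the high dose. That goes too far. SAP 4.6 analyses booster safety by actual treatment received, and the booster safety summaries in SAP 7.1.1 and 7.2.1 are not split by primary dose. Only booster immunogenicity is split that way (SAP 8). The SAP does not govern stopping rules, but it shows a natural reading. What remains is a wording ambiguity shared by criteria 3 to 5.

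**Conclusion.** The point holds as a drafting error with minor impact. One of the five criteria in 10.6.2 cannot fire for any of the expected 80 or so boosted participants, although the heading says it covers them. The gap of at least 157 days follows from the visit schedule alone; the nominal 228 to 259 days depends on the stated 8 to 9 months.

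The loss is confined to the automatic suspension, and the DSMB review it compels, for a post-booster cluster of related Grade 3 events that are neither SAEs nor AESIs. The documents do not support the broader inference that the Booster Phase lacks stopping rules or safety monitoring. Nor do they allow a calculation of how often the corrected rule would fire, since they give no event rate. The 3-to-31-day range for doses still open to suspension rests on the assumed September dates. The DSMB charter was not available and might contain a booster rule, but the protocol text would still need correcting.

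**What to change.** In the fifth criterion of Protocol 10.6.2, replace condition (1) with: *occurs within 36 days following the first vaccination or, counted separately, within 36 days following the booster vaccination*. The primary-series window is unchanged, and the words on separate counting prevent primary-series and post-booster cases from being added together.

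As a secondary clarification, add one sentence to 10.6.2: for post-booster events in criteria 3 to 5, all boosted participants form one dose group. This matches the single dose given and the SAP's booster safety summaries.

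The DSMB charter needs the same edits if it repeats the text. No visits or data are added, because unsolicited events are already noted in the e-Diary to Visit 10 and safety samples are already drawn at Visits 8 and 9. The downside is a possible additional suspension and DSMB review. Pooling all boosted participants makes three matching cases easier to reach than counting within primary dose groups, so the sponsor should adopt it knowingly.
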